## 8. Assessment of treatment efficacy and safety

- 8.1 Assessment of treatment efficacy
  - 8.1.1 All enrolled patients will receive assessment of tumor response by imaging studies every 12 weeks, according to RECIST version 1.1. Computed tomography is the preferred imaging modality and should include imaging of chest and abdomen at baseline and follow-up.
  - 8.1.2 For subjects who are considered suitable for surgical resection, the actual surgical procedure will be determined by individual treating surgeons and will be recorded. The time frame for holding the study drug prior to surgery will be determined by the treating physician. Participants may resume the study drug after recovery from surgery, at the physician's discretion.
- 8.2 Management of immune-related adverse events (irAE) 7,8
  - 8.2.1 The definition of the most irAE and according management recommendation are summarized in the following table.
  - 8.2.2 For the definition of hepatitis grading, only ALT (alanine aminotransferase) level is used because it is more specific to liver inflammation.
  - 8.2.3 Definition of study drug-induced liver injury (DILI) was listed below, according to the amendment #8 of the CA209040 protocol:
    - 8.2.3.1 Concurrent ALT  $\geq$  10 x ULN AND total bilirubin  $\geq$  2 x ULN or baseline value (if elevated bilirubin at study entry), AND
    - 8.2.3.2 No other immediately apparent possible causes of ALT elevation and hyperbilirubinemia, including, but not limited to, tumor progression, acute viral hepatitis, cholestasis, pre-existing hepatic disease or the administration of other drug(s), herbal medications and substances known to be hepatotoxic.
    - 8.2.3.3 Management of hepatic events, including dose delay and/or discontinuation as well as intervention with steroid treatment, will follow the recommendation listed below, will not be impacted by the definition of DILI.

Types of irAE	Grade 1	Grade 2	Grade 3	Grade 4
Hepatitis	ALT up to 3 x ULN AND > 2x baseline  • Monitor weekly  • Look for other causes of hepatitis (e.g., viral infections other than HBV/HCV, hepatotoxic drugs)	ALT 3 to 5 x ULN AND > 2x baseline If patient is well, re-check liver function every 2-3 days. Steroid treatment (e.g., prednisolone 1–2 mg/kg/day or IV equivalent) if no improvement or worsening. Taper steroids over 4 weeks once liver function G1 or at baseline	ALT 5 to 20 x ULN:  • As per Grade 2  • Delay study drug treatment if ALT≤ 8X ULN and bilirubin ≤ 5X ULN.  Discontinue if worse  • Steroid treatment (e.g., prednisolone 1–2 mg/kg/day or IV equivalent)  • Consider liver biopsy  • Consider prophylactic antibiotics for opportunistic infection	ALT >20 x ULN:  • Discontinue study drug administration  • As per Grade 3 (Steroid treatment at prednisolone 2 mg/kg/day or IV equivalent).  • Consult immunologists for additional immunosuppressive therapy (e.g. infliximab, mycophenolate, immunoglobulins).
Diarrhea/ enterocolitis	<4 bowel actions per day over baseline; mild: • Supportive measures such as increasing • Oral fluid • Anti-motility agents such as loperamide	
 
4–6 bowel actions per day over baseline; moderate:
 
Delay stud drug administration.
 
As per Grade 1 if patient is well.
 
Steroid treatment (e.g., prednisolone 0.5–1 mg/kg/day or IV equivalent) if no improvement in 5-7 days, or if worsening of symptoms; continue until symptoms improve to G1. Steroids can be tapered over 2–4 weeks.
 
If no improvement > 3-5 days with oral steroids, manage as per G3.
 
Consider sigmoidoscopy and biopsy
 
	≥7 bowel actions per day over baseline; severe symptoms:  • Discontinue study drug administration.  • Hospitalization and intravenous hydration  • Steroid treatment (e.g., prednisolone 1–2 mg/kg/day or IV equivalent.  • If no improvement in 2–3 days, consult immunologists for additional immunosuppressive therapy (e.g. infliximab, mycophenolate, immunoglobulins).  • If improving, taper steroids over minimum 1 month (up to 3 months for severe cases).  • Consider sigmoidoscopy and biopsy	Life threatening consequences (e.g., perforation)  • Urgent intervention indicated: as per G3.  • Involve gastroenterologist and surgeon in management.
Pneumonitis	Asymptomatic; Clinical observations; Consider delaying study drug administration. Consider steroids (e.g. prednisone 1 mg/kg/day PO or methylprednisolone 1 mg/kg/day IV). Re-image at least	Symptomatic; limits instrumental ADLs:  Delay study drug administration.  Consider hospitalization, daily monitoring of symptoms.  Steroid treatment (prednisone 1 mg/kg/day PO or IV	Severe symptoms; limits self-care ADLs; oxygen indicated:  • Discontinue study drug administration.  • Hospitalization.  • Steroid treatment (prednisone 2-4 mg/kg/day PO or IV equivalent).	Life-threatening respiratory compromise;  • Urgent intervention indicated (eg intubation): as per Grade 3.  • Intensive care support required

Endacrina	every 3 weeks.	equivalent).  Consider empiric antibiotics  Follow-up: reassess management every 1–3 days. If improving taper steroids.  May continue study drug treatment if symptoms resolve completely.	
 
Consider high-dose steroid treatment (e.g. methylprednisolone 1 g/day IV) (Spain L, et al. Cancer Treat Rev 2016).
 
Add prophylactic antibiotics for opportunistic infections.
 
Consider bronchoscopy with biopsy.
 
Reassess management daily. If not improving after 48 h or worsening, consult immunologists for additional immunosuppressive therapy (e.g. infliximab, mycophenolate, immunoglobulins). If improving, taper steroids.
 
	Life threatening
Endocrine dysfunction	Asymptomatic  • Monitor only  • Consider endocrinology consultation	Symptomatic  Consult endocrinologist  Levothyroxine replacement for hypothyroidism  Cortisol replacement for hypoadrenalism  Consider β-blockers for hyperthyroidism- related symptoms  Consider steroids or carbimazole for hyperthyroidism	
 
Severe symptoms:
 
As per grade 2.
 
Delay study drug administration.
 
Steroid treatment (e.g., prednisolone 1–2 mg/kg/day or IV equivalent)
 
	Life threatening consequences  • As per Grade 3.  • Delay or discontinue study drug administration.
Nephritis	Creatinine > 1X ULN and ≤1.5 X baseline; proteinuria 1+, <1.0g / 24 h:  • Monitor renal function weekly; hydration	Creatinine > 1.5–3.0 X baseline; proteinuria 2+, 1.0– 3.4 g/24 h: • Steroid treatment (e.g., prednisolone 0.5–1 mg/kg/day or IV equivalent) • Delay study drug administration. Monitor renal function every 2-3 days; If worsens, manage as per grade 3 • Exclude non-immune causes	Creatinine > 3.0 X baseline to ≤ 6X ULN; proteinuria ≥ 3.5 g/24 h:  • As per Grade 2  • Consider renal biopsy  • If elevations persist > 7 days or worsens, manage as per grade 4	Creatinine > 6.0 X ULN:  • Steroid treatment (e.g., prednisolone 1–2 mg/kg/day or IV equivalent)  • Consider renal biopsy • Discontinue study drug treatment
Skin rash	<10% BSA:	10–30% BSA:	>30% BSA:	Life threatening

Antihistamines and topical steroid for pruritus	
 
As per G1 if tolerable
 
If intolerable, steroid treatment (eg prednisolone 0.5–1 mg/kg/day with a 1–2 week wean)
 
Delay study drug treatment until G1 and steroids <10 mg/day
 
Consider skin biopsy if symptoms persist or recur
 
	
 
Consult dermatologist and consider skin biopsy
 
Steroid treatment (e.g., prednisolone 1 mg/kg/day or IV equivalent).
 
Delay study drug treatment until G1 and steroids <10 mg/day
 
	consequences • As per Grade 3.
---	---	--	--------------------------------

- 8.2.4 When irAE improved to Grade 1 after steroid treatment, may taper steroid dosage over at least 1 month.
- 8.2.5 For other grade 3-4 toxicities (according to CTCAE version 4) that are considered to be related to study drug treatment, study drug treatment should be held if the toxicities last for 3 days or more under best supportive care. Further study drug treatment may be considered when toxicity has resolved to ≤ grade 1, after discussion with the principal investigator.
- 8.2.6 Recent review of irAE indicated the clinical significance of the rare but potentially fatal cardiac toxicity for patients who received combination immunotherapy . Cardiac exam (echocardiography or radionuclide ventriculography (MUGA scan)) will be done at baseline, at the first imaging assessment, and at the end-of-treatment (EOT) evaluation. Troponin-T(or hs-cTnT), pro-BNP (brain natriuretic peptide), and creatinine kinase (CK) or CK-MB isoform (CK-MB) will be checked every 3 weeks before each administration of study drug treatment and at EOT evaluation.
- 8.2.7 When cardiac toxicity is suspected, cardiologists will be consulted for further diagnostic work-up. High-dose steroid and other immunosuppressive treatment will be used according to the most recent expert recommendation.
- 8.3 Patients will be followed every 3 weeks to evaluate the occurrence and severity of adverse events, according to CTCAE version 4.
- 8.4 The Institution and the Principal Investigator shall report any Adverse Events arising out of or in connection with the Study to the Regulatory Authority in accordance with applicable laws and regulations.
- 8.5 Serious adverse events (SAE) must be reported in written forms to the institutional review boards of the participating centers and Department of Health, Taiwan, within 7 working days. SAE is defined as any event that
  - 8.5.1 Results in death;
  - 8.5.2 Life-threatening (defined as an event in which the participant was at risk of death at the time of the event; it does not refer to an event which hypothetically might have caused death if it were more severe);
  - 8.5.3 Results in hospitalization or prolong inpatient hospitalization;
  - 8.5.4 Results in persistent or significant disability/incapacity;
  - 8.5.5 Results in congenital anomaly of offspring;

- 8.5.6 Requires treatments for permanent injuries;
- 8.5.7 Results in development of second malignancy. Second malignancy includes any second primary malignancy, regardless of causal relationship to the study drug, occurring at any time for the duration of the study, from the time of signing the informed consent up to 3 months after withdrawal from the study drug.
- 8.5.8 An important medical event (defined as a medical event(s) that may not be immediately life-threatening or result in death or hospitalization but, based upon appropriate medical and scientific judgment, may jeopardize the subject or may require intervention [eg, medical, surgical] to prevent one of the other serious outcomes listed in the definition above.) Examples of such events include, but are not limited to, intensive treatment in an emergency room or at home for allergic bronchospasm; blood dyscrasias or convulsions that do not result in hospitalization.
- 8.5.9 Results in suspected transmission of an infectious agent (e.g., pathogenic or nonpathogenic) via the study drug is an SAE.
- 8.5.10 Although pregnancy, overdose, potential drug-induced liver injury (DILI) and cancer are not always serious by regulatory definition, these events must be handled as SAEs. Overdose is defined as the accidental or intentional administration of any dose of study drugs that is considered both excessive and medically important.
- 8.6 If an ongoing SAE changes in its intensity or relationship to study drug or if new information becomes available, a follow-up SAE report should be sent within 24 hours to IRB. All SAEs should be followed to resolution or stabilization.
  - 8.6.1 An SAE report should be completed for any event where doubt exists regarding its seriousness.
  - 8.6.2 If the investigator believes that an SAE is not related to study drug, but is potentially related to the conditions of the study (such as withdrawal of previous therapy or a complication of a study procedure), the relationship should be specified in the narrative section of the SAE Report Form.
  - 8.6.3 If only limited information is initially available, follow-up reports are required. (Note: Follow-up SAE reports should include the same investigator term(s) initially reported.)
  - 8.6.4 Definition of SAE is listed in Section 10.5. Additional description of SAE, as required by the study drug supplier, is listed below.
    - 8.6.4.1 Any component of a study endpoint that is considered related to study therapy should be reported as an SAE (eg, death is an endpoint, if death occurred due to anaphylaxis, anaphylaxis must be reported).
    - 8.6.4.2 The following hospitalizations are not considered SAEs in this study:
    - 8.6.4.3 A visit to the emergency room or other hospital department < 24 hours, that does not result in admission (unless considered an important medical or lifethreatening event)
    - 8.6.4.4 Elective surgery, planned prior to signing consent
    - 8.6.4.5 Admissions as per protocol for a planned medical/surgical procedure
    - 8.6.4.6 Routine health assessment requiring admission for baseline/trending of health status (e.g., routine colonoscopy)

- 8.6.4.7 Medical/surgical admission other than to remedy ill health and planned prior to entry into the study. Appropriate documentation is required in these cases
- 8.6.4.8 Admission for administration of anticancer therapy in the absence of any other SAEs (applies to oncology protocols)
- 8.6.5 An Adverse Event (AE) is defined as any new untoward medical occurrence or worsening of a preexisting medical condition in a clinical investigation participant administered study drug and that does not necessarily have a causal relationship with this treatment. An AE can therefore be any unfavorable and unintended sign (such as an abnormal laboratory finding), symptom, or disease temporally associated with the use of investigational product, whether or not considered related to the investigational product.
- 8.6.6 The causal relationship to study drug is determined by a physician and should be used to assess all adverse events (AE). The casual relationship can be one of the following:
  - 8.6.6.1 Related: There is a reasonable causal relationship between study drug administration and the AE.
  - 8.6.6.2 Not related: There is not a reasonable causal relationship between study drug administration and the AE.
  - 8.6.6.3 The term "reasonable causal relationship" means there is evidence to suggest a causal relationship.
  - 8.6.6.4 Adverse events can be spontaneously reported or elicited during open-ended questioning, examination, or evaluation of a subject. (In order to prevent reporting bias, subjects should not be questioned regarding the specific occurrence of one or more AEs.)
  - 8.6.6.5 Nonserious AE information should also be collected from the start of a placebo lead-in period or other observational period intended to establish a baseline status for the subjects.
  - 8.6.6.6 The collection of nonserious AE information should begin at initiation of study drug. All nonserious adverse events (not only those deemed to be treatment-related) should be collected continuously during the treatment period and for a minimum of 30 days following the last dose of study treatment.
  - 8.6.6.7 Nonserious AEs should be followed to resolution or stabilization, or reported as SAEs if they become serious. Follow-up is also required for nonserious AEs that cause interruption or discontinuation of study drug and for those present at the end of study treatment as appropriate.
- 8.6.7 All laboratory test results captured as part of the study should be recorded following institutional procedures. Test results that constitute SAEs should be documented and reported as such. The following laboratory abnormalities should be documented and reported appropriately:
  - 8.6.7.1 any laboratory test result that is clinically significant or meets the definition of an SAE
  - 8.6.7.2 any laboratory abnormality that required the participant to have study drug discontinued or interrupted

- 8.6.7.3 any laboratory abnormality that required the subject to receive specific corrective therapy.
- 8.6.8 Other Safety Considerations: Any significant worsening noted during interim or final physical examinations, electrocardiograms, X-rays, and any other potential safety assessments, whether or not these procedures are required by the protocol, should also be recorded as a nonserious or serious AE, as appropriate, and reported accordingly.

## 9. Analysis of predictive markers

- 9.1 Biomarker study of the pre-treatment biopsy tumor tissue
  - 9.1.1 Five 10-micrometer-thick slides will be obtained from paraffin-embedded tumor specimens for DNA/RNA extraction and subsequent whole exome sequencing and RNA sequencing.
  - 9.1.2 Ten 4-micrometer-thick slides will be obtained from paraffin-embedded tumor specimens for tissue staining. Immunohistochemistry or multiplex staining will be done in paraffin-embedded tumor specimens if enough tissue samples are available to confirm the proportion and distribution of immune cells in different tumor microenvironment.
- 9.2 Biomarker study of peripheral blood samples during study drug treatment
  - 9.2.1 For the immunology study, peripheral blood samples will be collected before the start of the first cycle of study drug treatment, at the time of tumor response assessment, and at the end-of-treatment assessment.
  - 9.2.2 Blood samples will be put in BD Vacutainer®CPT™ cell preparation tubes and EDTA tube respectively, and centrifuged within 6 hours after sampling.
  - 9.2.3 The mononuclear cell layer will be stored in liquid nitrogen for flow cytometry and DNA/RNA extraction studies.
  - 9.2.4 Flow cytometry and transcriptomic analysis will be done to analyze the proportion of different immune cells in peripheral blood and the results will be correlated with efficacy of study drug treatment.
  - 9.2.5 Plasma will be used for blood biomarker research including but not limited to cfDNA, cytokine and lipid profiling.
- 9.3 Biomarker study of the resected tumor tissue from subjects who undergo surgery
  - 9.3.1 Samples from the same tumor(s) will be obtained from formalin-fixed, paraffinembedded tumor specimen for relevant studies
  - 9.3.2 The genetic study to be done include but not limited to whole exome sequencing.
  - 9.3.3 Transcriptomic analysis will be done to analyze the composition (e.g., the proportion of different immune cells) of the immune microenvironment by using RNA-Seq and the results will be correlated with efficacy of study drug treatment.
  - 9.3.4 The biomarker studies of tumors and peripheral blood samples will be done at the National Health Research Institutes. The relevant information of the responsible laboratory is as follows:
    - Name of the institution/laboratory: National Institute of Cancer Research.
    - Mailing address: [name]

## 10. Criteria for discontinuation of study drug treatment

Discontinuation of study drug treatment is when a patient no longer receives study drug but continues to be followed up for tumor status and survival according to local treatment guidelines for up to half year, unless consent is withdrawn. Patients may be discontinued from study drug treatment and assessments at any time. When study drug treatment is discontinued due to the reasons listed below, no further AHCC/placebo treatment will be provided by this study and further anticancer therapy will be decided by the investigators according to current treatment guidelines. Specific reasons for discontinuation of study drug treatment include:

- 10.1 Voluntary discontinuation by the subject who is at any time free to discontinue his/her participation in this study, without prejudice to further treatment.
- 10.2 When the investigator(s) consider other treatment modalities (surgery, others) are more suitable for the subjects according to assessment of tumor response specified in the protocol.
- 10.3 Safety reasons as judged by the investigator. Severe non-compliance to protocol as judged by the investigator.
- 10.4 Incorrect enrollment, in the opinion of the investigator or study delivery team physician, which will compromise the patient's health if study drug treatment or assessments are continued.
- 10.5 Dose delay or interruption of study drug treatment for more than 3 weeks.

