Following the Screening period to confirm eligibility, 98 study participants, who meet the entry criteria, will be 1:1 randomized to study intervention (3g of AHCC oral per day or matching placebo) and will be stratified by AFP (<400 vs. ≥400). Enrollment is anticipated to be completed within 2 years, with each participant followed for 6 months since treatment. Therefore, the total duration of the study is expected to be approximately 2.5 years from the time of Institutional Review Board approval. All enrolled participants will receive AHCC or placebo 3g per day until disease progression, intolerance or patient or physician decision to discontinue. Tumor tissue and peripheral blood samples will be collected from all participants for biomarker analysis.

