## 7. Treatment and follow-up plan

- 7.1 All enrolled patients will receive AHCC or placebo 3g every day until disease progression, intolerance or patient or physician decision to discontinue.
- 7.2 During treatment the subjects will be followed according to the follow-up plan summarized in the following table:
  - 7.2.1 Hematology and biochemistry levels will be checked within 72 hours before each administration of study drug treatment.
  - 7.2.2 A window of +/- 7 calendar days is allowable for imaging examination for tumor assessment.
  - 7.3 Prohibited treatment during the study drug treatment period includes the following:
    - 7.3.1 Investigational agents for the treatment of cancer;

7.3.2 Systemic steroids > 10 mg within 14 days of dosing (with a few exceptions eg, steroids for adrenal insufficiency, steroids if taken as part of prophylaxis for CT prep).

	Screen	Treatment Cycles (21-day cycles)					End-of-treatment
	Screen						(EOT) evaluation a
		C1 C2		C3	C4	C5	4 weeks after last
Week		C6	C7	C8	C9	C10	treatment
		:	:	:	:	:	treatment
Informed consent	Х						
Inclusion/exclusion criteria	Х						
Demography/ tumour staging	X						
Medical history	X						
Vital signs	X	Х	Х	Х	Х	Х	X
ECG	X						X
Blood test b	Х		Х	Х	Χ	Χ	Х
Urinalysis	Х					Х	X
HBV/HCV serology markers c	Х						Х
Performance status	Х	Х	Х	Х	Χ	Х	X
Chest X-ray	Х						X
Tumor assessment d	Х					Χ	
Treatment		Х	Х	Х	Х	Х	
Pregnancy test e	Х						
lmmunological study f	Х					Х	Х
Thyroid function g	Х						Х
Tolerability/AE reporting		Χ	Χ	Χ	Х	Х	Х
QOL questionnaire	Х			Х		Χ	Х

- a) The EOT assessment will take place at approximately 1 month after last treatment.
- b) Blood tests will include CBC/DC, albumin, total and direct bilirubin, transaminases (AST and ALT), ALP, AC sugar, sodium, blood urea nitrogen (BUN), creatinine, amylase, lipase, Troponin-T(or hs-cTnT), pro-BNP (brain natriuretic peptide), and creatinine kinase (CK) or CK-MB isoform (CK-MB). Other biochemistry tests may be done at the discretion of individual investigators.

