### 11. Statistical consideration

- 11.1 The primary endpoint is ORR in AHCC arm compared to placebo arm. The secondary endpoints include, incidence and severity of adverse events according to CTCAE version 4, progression-free survival and overall survival.
- 11.2 Exploratory endpoints will include correlation of treatment response (tumor shrinkage, objective response rate, etc.) with immune biomarkers in subjects' samples from tumor tissue and peripheral blood.
- 11.3 We simultaneously monitor efficacy and safety endpoints using the 2-arm Bayesian optimal phase 2 (BOP2) design (Zhao et al., 2020).
- 11.3.1 Specifically, let n denote the interim sample size and N denote the maximum sample size. Let E and C denote the experimental arm and the control arm, respectively. For arm t, t = E, C, let  $Y_{eff,t}$  and  $Y_{tox,t}$  respectively denote the efficacy and toxic endpoints, with  $Y_{eff,t} = 1$  and  $Y_{tox,t} = 1$  respectively indicating that patients experience efficacy and toxicity. We assume that the joint distribution of  $\left(Y_{eff,t}, Y_{tox,t}\right)$  follows a multinomial distribution with four elementary

the joint distribution of  $(1_{eff,t},1_{tox,t})$  follows a martinormal distribution with four elementary

outcomes:  $\left(Y_{eff,t},Y_{tox,t}\right)$  = (1, 1), (1, 0), (0, 1) and (0, 0). Let  $\mathbf{p_t} = \left(P_{11,t},P_{10,t},P_{01,t},P_{00,t}\right)$ 

denote the probabilities of observing the four outcomes, and let  $p_{eff,t} = Pr(Y_{eff,t} = 1)$ ,

$$p_{tox,t} = Pr(Y_{tox,t} = 1)$$
 and  $p_{efftox,t} = Pr(Y_{eff,t} = 1, Y_{tox,t} = 1)$ .

11.3.2 The experimental arm is deemed as unacceptable if  $H_0$ :  $p_{eff,E} \leq p_{eff,C}$  or  $p_{tox,E} > p_{tox,C}$ , i.e., the experimental treatment is inefficacious or overly toxic, with respect to the control. We employ the following Bayesian rule to make a go/no-go decision: (Futility and toxicity stopping) stop enrolling patients and claim that the experimental arm is unacceptable if

$$Pr(p_{eff,E} > p_{eff,C}|data) < \lambda \left(\frac{n}{N}\right)^{\alpha}$$
,

[figure not shown]
OR

$$Pr(p_{tox,E} \leq p_{tox,C}|data) < \lambda \left(\frac{n}{N}\right)^{\alpha}$$
,

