- 11.4 The primary endpoint analysis and other secondary endpoints will be based on the intent-to-treat population and per-protocol population, while the safety data will be summarized based on the intent-to-treat population.
  - 11.4.1 Intent-to-treat population refers to all enrolled patients regardless of their compliance with the study drug treatment.
- 11.4.2 Per-protocol population refers to all patients who have received at least 6 weeks (2 cycles) of study medication and received the first scheduled assessment of tumor response.
  - 11.5 Disease stabilization rate (complete response + partial response by RECIST + stable disease by RECIST that last for  $\geq 8$  weeks), objective response rate (complete response + partial

- response by RECIST), and down-staging rate will be calculated with their 95% confidence intervals.
- 11.6 Progression-free survival, time-to-tumor progression, and overall survival will be calculated by the Kaplan-Meier method.
- 11.6.1 Progression-free survival is defined as the duration from the date of the first dose of study drug treatment to the date of documented disease progression or death of any cause.
- 11.6.2 Time-to-tumor progression is defined as the duration from the date of the first dose of study drug treatment to the date of documented tumor progression by imaging studies.
- 11.6.3 Overall survival is defined as the duration from the date of the first dose of study drug treatment to the date of death of any cause.
  - 11.7 The baseline and changes in immune-related biomarkers after study drug treatment will be correlated with the patients' treatment outcome, including disease stabilization, best radiographic response, time to tumor progression, progression-free survival, and overall survival.
  - 11.8 For the endpoint of the safety assessment, the tabulations will count the number of subjects reporting individual adverse events. Incidence of adverse events and serious adverse events will be summarized.
  - 11.9 The demographic features of the subjects will be summarized by descriptive statistics. Comparison between sub-groups, for examples, subjects with vs. without objective tumor response/AFP response/disease stabilization subjects with vs. without surgery after study drug treatment by using Mann-Whitney tests/ one-way ANOVA (continuous variables) or chisquare/Fisher's Exact tests (categorical variables).

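### The survival follow-up period is fixed by two unreconciled clocks, one from treatment and one from stopping study drug, and either would weaken the overall survival estimate

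*Protocol*

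**What the plan says.** Three parts of the protocol bear on how long survival is followed.

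- **Section 1 (Abstract):** "Enrollment is anticipated to be completed within 2 years, with each participant followed for 6 months since treatment". From this the protocol concludes that "the total duration of the study is expected to be approximately 2.5 years from the time of Institutional Review Board approval".
- **Section 10 (Criteria for discontinuation):** a patient who no longer takes study drug "continues to be followed up for tumor status and survival according to local treatment guidelines for up to half year". Section 7.1 sets no fixed treatment length: "All enrolled patients will receive AHCC or placebo 3g every day until disease progression, intolerance or patient or physician decision to discontinue".
- **Section 11:** OS is a secondary endpoint (11.1). Under 11.6.3, "Overall survival is defined as the duration from the date of the first dose of study drug treatment" to death of any cause, and under 11.6 "Progression-free survival, time-to-tumor progression, and overall survival will be calculated by the Kaplan-Meier method". No common survival cut-off date is given.

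**The concern.** The abstract's clock appears to start with treatment and the Section 10 clock starts when treatment ends. For a patient who stays on drug for a year, the first ends survival follow-up at month 6 and the second at up to month 18.

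The choice matters in different ways:

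- If the abstract governs, patients enrolled early leave follow-up while the trial stays open for up to 24 more months, and their later deaths are never recorded.
- If Section 10 governs, progression stops the drug, and stopping the drug starts the countdown to the end of survival follow-up. Patients who progress early have a worse outlook and are censored first. Kaplan-Meier requires censoring to be unrelated to prognosis, so the OS curve would be too high.

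Follow-up length is fixed by the protocol. An analysis plan cannot recover deaths that were never collected.

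**Working it through.** **1. The protocol's own figure.** 24 months of accrual + 6 months of follow-up = 30 months = 2.5 years, so the stated duration reproduces. It does so if the 6 months run from treatment start. If they run from the end of treatment, a patient enrolled at month 24 and treated for d months needs follow-up to month 24 + d + 6 = 30 + d, which overruns for any d above zero.

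**2. Inputs.** From the protocol: N = 98, 24 months of accrual, end at month 30. Assumed: uniform accrual starting at the beginning of the 2.5 years, so that potential follow-up is uniform between 6 and 30 months; and the survival medians below. The protocol gives no median OS, OS event target or OS power.

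**3. Abstract rule, 6 months from treatment start.** Exponential OS with median m and h = ln 2 / m.

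- Deaths with the cap: 98 × (1 − e^(−6h))
- Deaths with follow-up to month 30: 98 × [1 − (e^(−6h) − e^(−30h)) / (24h)]

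For m = 12: h = 0.05776, e^(−6h) = 0.7071 and e^(−30h) = 0.1768. With the cap, 98 × 0.2929 = 28.7. To month 30, 98 × (1 − 0.5303/1.3863) = 60.5. Share lost: 1 − 28.7/60.5 = 53%.

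| Assumed median OS (months) | Deaths, 6-month cap | Deaths to month 30 | Lost |
|---|---|---|---|
| 6 | 49.0 | 81.4 | 40% |
| 9 | 36.3 | 69.9 | 48% |
| 12 | 28.7 | 60.5 | 53% |
| 18 | 20.2 | 47.2 | 57% |
| 24 | 15.6 | 38.6 | 60% |

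The loss passes one half at a median of about 10 months. Every patient has the same administrative censoring time, so Kaplan-Meier is unbiased to month 6. It says nothing beyond that.

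**4. Section 10 rule, drug stop + 6 months.** Simulation of 400,000 patients. OS is an exponential time to progression plus an exponential post-progression survival. Drug stops at progression, and OS is censored 6 months later or at month 30, whichever is first. Death counts are scaled to 98 patients.

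| Assumed medians: to progression / after (months) | Median OS | Deaths, this rule | Deaths to month 30 | Lost | S(12): KM vs true | S(18): KM vs true |
|---|---|---|---|---|---|---|
| 4 / 6 | 12.0 | 42.3 | 64.8 | 35% | 0.54 vs 0.50 | 0.37 vs 0.29 |
| 6 / 8 | 16.9 | 30.4 | 49.6 | 39% | 0.70 vs 0.66 | 0.56 vs 0.47 |
| 6 / 10 | 19.1 | 25.4 | 44.1 | 42% | 0.75 vs 0.71 | 0.62 vs 0.53 |

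Two longer pairs (6 / 12 and 8 / 12) lose 45% and 44%, with the same direction of bias. In the 6 / 10 case about 33 of 98 patients, both arms together, are at risk at month 12 and about 11 at month 18.

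**5. With a common cut-off, 6 / 10 case.** The number at risk is 98 × (30 − t)/24 × S(t). At month 12: 98 × 0.75 × 0.714 = 52. At month 18: 98 × 0.5 × 0.531 = 26. Censoring then depends only on entry date, and the progression-triggered bias is gone.

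Steps 3 and 4 use different survival models, so their death counts should not be combined. In the progression-then-death models the 6-month cap loses 69-81%, more than the exponential range.

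**The case against.** **The wording is ambiguous rather than flatly contradictory.** The abstract's phrase could mean since the end of treatment, and would then agree with Section 10. This stands in part. That reading makes 2.5 years too short for anyone still on drug when accrual closes, and it leaves the progression-triggered censoring in place.

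**The two harms cannot both occur.** This stands. The loss in step 3 and the bias in step 4 belong to different rules.

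**A reader might infer that more than half of the deaths are certainly discarded.** The documents do not support this. They state no median OS, and under exponential survival the loss is 40% at a median of 6 months and 48% at 9.

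**A reader might take the bias at 24 months as the headline** (0.52 against 0.38 in the 6 / 10 case). Only about 2.7 of 98 patients would be at risk then, and the sampling standard deviation of a 49-patient arm's estimate is about 17 points, more than the 14-point bias. At month 12 the bias is about 3.5 points against a standard deviation of about 7. The bias is systematic, but at 12 months it is smaller than the sampling noise.

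**A reader might infer a biased treatment comparison or an imprecise hazard ratio.** Section 11 specifies no OS hazard ratio or test. The rule applies equally to both blinded arms. A comparative bias depends on whether time on drug differs by arm, and none has been shown.

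**OS is secondary, and its detailed censoring rules may sit in an analysis plan.** This is true of the details, but the length of data collection is a protocol matter.

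**Conclusion.** The point holds as an inconsistency to be reconciled, with a real but conditional cost to a secondary endpoint. Under the abstract's clock counted from treatment start, about 40-60% of the deaths observable by month 30 are not collected, for exponential OS with assumed medians of 6 to 24 months. Under Section 10's clock, about 35-42% are lost in the three cases tabulated, and the Kaplan-Meier OS curve is too high by about 4 points at 12 months and 8 to 10 points at 18 months. The second set of figures assumes that drug stops only at progression and that follow-up lasts the full half year; Section 10 sets that as a maximum, so actual follow-up could be shorter.

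The objective response rate decision is unaffected, because the go/no-go rule in Section 11.3 uses response and toxicity only. The change is worth making, but the trial's main conclusion does not depend on it.

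**What to change.** Put the same rule in Section 1 and Section 10: every randomised patient is followed for survival to one common cut-off, 6 months after the last patient is randomised, regardless of when study drug stopped. OS is censored only at that cut-off, at withdrawal of consent, or at loss to follow-up.

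The cost is survival-status contacts for the earlier enrollees within the planned 2.5 years. The trial gets no longer and needs no more patients. If follow-up for progression is also to run to the common cut-off in patients who have stopped drug without progressing, the existing 12-weekly imaging would have to continue for them. The protocol should name that cost and say whether it is intended.
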